- Apple: During G6 setup, enable Dexcom app notifications or you won't get alarm/alerts.

Battery: The app must always be running in the background and may

drain your smart device battery. Keep the battery charged.

Compatibility: Before upgrading your smart device or its operating system, check dexcom.com/compatibility. Automatic updates of the app or your device operating system can change settings or shut down the app. Always update manually and verify correct device settings afterward.

Time: Let the date and time on your smart device automatically update when you travel across time zones or switch between standard and daylight saving times. Don't manually change your smart device time, because it can make the time on the trend screen wrong and the app may stop displaying data.

Precautions

Check Peripheral Devices

Do you use headphones with your smart device? What about Bluetooth speakers or a smart watch? When using peripherals, keep in mind you may get your alarm/ alerts on only one device or peripheral, not all. After connecting any peripheral devices, make sure that your smart device settings allow you to continue receiving alarms or alerts.

Receiver Safety Statements

Warnings

Don't Use if Damaged

Don't use a receiver that is damaged or cracked. A damaged receiver could cause injuries from electrical shocks and may make the G6 not work correctly.

Use Cable as Directed

Use USB cable only as directed, and store safely. Misuse of the USB cable can be a strangulation risk.

Follow G6 instructions. If you don't, you could have a severe low or high glucose event.

Precautions

Test Speaker and Vibrations

You have to hear or feel alarm/alerts to react to them, so test your receiver speaker and vibrations regularly.

To make sure the speaker and vibrations work, plug in the receiver to charge. The Speaker Test screen appears for a few seconds. Follow the directions on the screen to test the speaker and vibrations. If you hear and feel them, great! But if it doesn't beep and vibrate – perhaps it got wet or was dropped – contact Technical Support and use your app until the receiver is fixed.

Keep Clean and Dry

Don't submerge your receiver in water and don't get dirt or water in the USB port. That could damage it.

Dexcom Share Safety Statements

Important User Information

Dexcom Share (Share) lets you send your sensor information from your app to your Followers' smart devices! Read the indications, warnings, and precautions below to find out how you can safely use this app feature.

Share and Managing Your Diabetes Safety Statements

Indications

Keep Followers Informed

Use Share to send your sensor information from your smart device to your Followers' smart devices.

Use as Secondary Notice

The information on your smart device is sent directly from your G6 transmitter. After it is on your device, Share sends it to your Followers. So your Followers' information is always older than yours. Use your current information to manage your diabetes, not your Followers' possibly outdated information.

Your Followers can use the information they get to reach out to you and support you in managing your diabetes. The information they get is not meant to be used for treatment decisions, analysis, or teaching. Followers can't change your information.

NB sharing will be disabled during the study, except during the unblinded phase of arm 2

Risk mitigation strategies discussed above.

Trial subjects will be counselled on the above side effects and how to manage them. The endocrine team at St Bartholomew's hospital is contactable 24 hours/day – either through the ward team in 5B ward (0900-1700) or through an on-call endocrine registrar (1700-0900) for all endocrine patient and GP enquiries.

We will include side effect occurrences as part of our monthly study management meetings and will introduce additional methods if it becomes clear that these are required.

12. Statistical considerations

This is a non-randomised study with a small (30 patients) population, no statistician involvement will be required.

12.1 Sample size

30 patients

This is intended to be a pilot study to test the feasibility of using CGM for this purpose. It may in future complement (or in some instances replace) inpatient investigation of hypoglycaemia.

The inpatient investigation of hypoglycaemia is relatively uncommon, even within tertiary centres. Spontaneous hypoglycaemia requiring medical treatment is similarly uncommon, even in tertiary centres.

12.2 Method of analysis

P<0.05 will be considered statistically significant

Arm 1

Positive and negative predictive value of CGM diagnosis of hypoglycaemia as an outpatient or an inpatient vs 72 hour fast (considered the 'gold standard')

Arm 2

In each patient, comparison of number of episodes of hypoglycaemia by finger prick glucose vs CGM vs symptoms during CGM blinded phase.

Severity of hypoglycaemia excursions

Amount of time spent in the hypoglycaemic range after medication titration – as measured by area under the curve on a time vs glucose graph generated by CGM machine. Comparisons of mean hypoglycaemic frequency and time within hypoglycaemic range within patients (blinded vs unblinded phase) using paired T test.

Change in hypoglycaemia questionnaire score before/after CGMs monitoring and medication titration

Regain of symptomatic hypoglycaemia in patients with asymptomatic hypoglycaemia, reduction of symptomatic hypoglycaemia in other patients.

13. Ethics

- Informed consent

Patients will be offered the chance to partake in the study should their treating consultant feel that they meet the inclusion criteria. Declining an invitation to take part in the study or leaving at any time means that the patient will default back to standard of care investigations. Their care will not be prejudiced or compromised in any way through either taking part or not taking part in the study.

- Recruitment

Only patients under investigation/treatment for hypoglycaemia at St Bartholomew's hospital will be considered for entry to the study. Patient being treated/investigated elsewhere who wish to be considered for the study would need to have their care transferred to St Bartholomew's by their GP/current endocrinologist.

- Inclusion / exclusion criteria

Inclusion/exclusion criteria is intended to screen out patients who have conditions that may affect their blood glucose (Diabetes Mellitus, underlying hepatic pathology) or in whom CGM is not recommended (pregnancy, critical illness) or in whom hypoglycaemia may be caused by extrinsic factors such as Diabetes medication.

- Study design

Aside from the wearing of a CGM device and completion of modified Clarke and Gold hypoglycaemia questionnaire (arm 2), all treatment is ‘standard of care’. In arm 1 (and, initially, arm 2) Patients and investigators are blinded to the CGM readouts. Patients are provided (as is usual) with finger prick glucose meters that they can use to check their blood sugar should they develop symptoms that they attribute to hypoglycaemia. The patients are therefore not disadvantaged by the ‘blinding’ process.

- Risks, burdens, and benefits

Patients will be counselled about (the few) risks associated with use of the Dexcom device, the main risks are those of infection from insertion of the probe under the skin and the risk of retained parts upon removal of the probe – and how to minimise these risks. The device is worn and as such may restrict the wearer’s choice of clothing and place some minor limitations on physical activity – mainly laying on top of the probe or engaging in close contact activities which might disrupt the probe’s positioning.

- Confidentiality

All patients recruited for the study will already be under the medical care of the endocrine team at St Bartholomew’s hospital, the study team is made up of staff from this department and they will therefore already have legitimate access to medical records and pathology results.

Any published data arising from this study will be anonymised.

Any data shared with Dexcom will be pseudonymised – each participant will receive a study number which will not be related to any of their identifiable details (name/DOB/address/NHS or hospital number).

- Conflicts of interest.

Dexcom will provide the study team with free receivers, transmitters, consumables and training in their equipment’s use. They have not had any influence on the study design, but have reviewed our design internally prior to granting approval for provision of the above equipment.

Dexcom will be allowed to share the data that we obtain, which will be pseudonymised. They will also be allowed to view the manuscript of any work (containing anonymised data) prior to submission to a peer reviewed journal, so that they can make suggestions but will not be the determining factor in the decision to submit work arising from this study for publication. This decision will reside with the study team and be based on scientific merit of the findings.

No other members of the study team have any relevant conflicts of interest.

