	
hypoglycaemia in order to improve outpatient management and improve patient safety. The Dexcom system has an alarm to alert patients to hypoglycaemia which will be used in the unblinded phase.
 
Aims
 
There will be two main arms to the study;
 
 1) Investigation of patients suspected of having hypoglycaemia (spontaneous or reactive) alongside standard investigations 2) Management of patients with confirmed hypoglycaemia who are medically managed to see if continuous glucose monitoring can play a role in abolishing asymptomatic hypoglycaemia through optimisation of medicines.
Number of participants	30
Inclusion and exclusion criteria	
Inclusion Criteria
 
Able and willing to give informed consent. No vulnerable adults will be included.
 
Either conventional gender, or non-binary.
 
Age >18 years
 
Any ethnicity
 
Any socio economic group
 
Medical condition as detailed above – arm 1 under investigation for possible/probable hypoglycaemia
 
Arm 2 – on medical therapy for established hypoglycaemia
 
Exclusion criteria
 
Unwilling or unable to give consent
 
Unable to speak sufficient English to give consent and understand study requirements
 
Age<18 or >90 years
 
Lack of capacity to consent
 
Underlying hepatic condition
 
Current excessive alcohol consumption (men regularly consuming >50 units/week, women >35 units/week)
 
Diabetes Mellitus
 
Current use of Diabetic medication or insulin
 
Currently pregnant
 
Any patient on haemo or peritoneal dialysis

Statistical methodology and analysis (if applicable)	
Study duration	1 year

5. Introduction

Suspected reactive and spontaneous hypoglycaemia can be a challenging problem to investigate. Definitive diagnosis currently relies upon the patient experiencing symptoms, reporting them accurately and then a series of complex investigations.

Current standard of care tests

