Current 'gold standard' testing when reactive hypoglycaemia is suspected is with an extended oral glucose tolerance test or mixed meal test. Where spontaneous hypoglycaemia is suspected and where facilities exist, the 'gold standard' test is an admission to Hospital for a 72 hour fast with twice daily laboratory measurements of plasma glucose, insulin and c-peptide. Finger prick glucose measurements are taken throughout the day to check for asymptomatic hypoglycaemia. Additional laboratory measurements are made if the patient becomes symptomatic. The prolonged fast is terminated when a diagnostic laboratory glucose measurement of $<2.2\text{mmol/L}$ is reached. Where a 72 hour fast is not possible, attempts are made to test insulin and glucose after three separate 15 hour fasts but this risks out of hospital hypoglycaemia and all its potential sequelae. These investigations attempt to mimic the situations which precipitate the hypoglycaemia but, in particular for reactive hypoglycaemia, often fail to do so.

Pathophysiology and significance of hypoglycaemia

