5.4 Rationale

Prompt diagnosis of hypoglycaemia is important as, untreated, it can lead to weight gain, symptomatic hypoglycaemia and increases the risk of sudden death through arrhythmia. At present, diagnosis of hypoglycaemia depends upon the reporting of symptoms and capture of hypoglycaemic range CBGs through finger prick glucose measurement. If the clinical suspicion of hypoglycaemia is strong enough, then patients will be admitted for a supervised 72 hour fast, where blood glucose is checked regularly through finger prick measurements and venous phlebotomy. Patients can lose hypoglycaemic awareness, however, and so symptoms are not always a reliable way to diagnose the problems. 72 hour fasts are labour intensive for the medical and nursing teams and may require the patient to take time off work or away from caring duties. A robustly tested CGM test may allow us to determine if blinded CGM testing can be used to obviate the need for inpatient testing. It may also provide useful diagnostic information by relating the proximity of hypoglycaemic episodes to food intake, adding to weight to diagnoses of reactive or spontaneous hypoglycaemia.

CGM has revolutionized the lives and medical management of type 1 Diabetes patients with hypoglycaemic unawareness and we hope that it can produce similarly excellent results in the field of reactive/spontaneous hypoglycaemia.

Once spontaneous hypoglycaemia has been diagnosed, treatment with medical therapy is often the first step. The goal is to try and make the patient hypoglycaemia free. This is tricky if the patient has no hypoglycaemia awareness, but can be overcome during the day with regular fingerprick glucose checks – though patients frequently complain that this is painful. At night, however, patients are asleep and

cannot check their blood glucose this way and so there is a paucity of data about their glycaemic state at night – the very time that they are fasting and hypoglycaemia is more probable. CGM can therefore tell us about their glycaemic status all day, without painful finger prick testing and also during the night whilst the patient is asleep. This information can then help doctors titrate their anti-hypoglycaemia medication with the aim of abolishing their hypoglycaemic episodes.

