6.1 Primary objective

- 1) Use CGM (blinded to the patient and investigator) in advance of standard investigations (where possible) in order to record whether patient symptoms correlate with recorded hypoglycaemia. This may exclude hypoglycaemia as a cause of symptoms and allow the patient to avoid a prolonged inpatient investigation.
- 2) Use CGM technology (blinded to the patient and investigator) alongside standard investigations for patients with both reactive and spontaneous hypoglycaemia to evaluate the relative efficacy of the two methods in detecting hypoglycaemia episodes.
- 3) Use CGM (blinded to the patient and investigator) to record frequency of hypoglycaemia after medical treatment has been initiated in order to assess its

effectiveness in detecting hypoglycaemic episodes of which the patient may not have been aware, potentially reducing the need for painful fingerprick glucose testing.

4) Use CGM (unblinded) to titrate medication to abolish hypoglycaemia in order to improve outpatient management and improve patient safety. The Dexcom system has an alarm to alert patients to hypoglycaemia which will be used in the unblinded phase.

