Once a date has been set for their admission to hospital for standard of care investigation of hypoglycaemia (usually including an oral glucose tolerance test or mixed meal test, but certainly including a 72 hour fast), an appointment will be made with the patient for 5 days prior to this date.

At this appointment, the patient will be provided with a finger prick glucose monitoring kit (and instructed in how to use it), a glucose monitoring diary to record finger prick glucose measurements and a CGM device. A CGM probe will be fitted during the consultation and checks made to ensure that it is working.

The patient will then proceed with their standard of care admission five days later. CGM monitoring will continue for the duration of their admission. The CGM device will be removed at discharge or after 5 days of admission, whichever comes first.

For patients who are transferred to St Bartholomew's directly for investigation of their hypoglycaemia, informed consent will be obtained at the earliest convenient point in their admission and the CGM device applied in preparation for the standard of care investigations. The CGM device will be removed at discharge or after 5 days of admission, whichever comes first.

Schedule of study interventions

Study intervention	Visit 1	Visit 2	Visit 3
Establishment of possible hypoglycaemia diagnosis	x		
Meet with study team to learn about study and give Informed consent	Either x	Or x	
Placement of CGM device, receive finger prick glucose meter and diary		x	
Admission to hospital for standard of care investigations Return CGM receiver device if not proceeding to arm 2			x

Arm 2

For patients with confirmed hypoglycaemia, where it is planned that they will receive medical management, we will seek informed consent for their entry into arm 2 of the study.

This might take place;

- at the conclusion of inpatient investigations for hypoglycaemia prior to initiation of anti-hypoglycaemia medication (on an inpatient or outpatient basis)
- after an endocrinology outpatient appointment for a patient with confirmed hypoglycaemia

In the first instance, patients will be fitted with a CGM device and given a finger prick glucose monitoring kit and glucose monitoring diary. Each patient will be asked to complete a modified Clarke and Gold hypoglycaemia questionnaire.

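### Section 12.2 scores every arm 1 CGM diagnosis against the 72-hour fast alone, though the protocol names a different gold standard for reactive hypoglycaemia and enrols both types

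*Protocol*

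**What the plan says.** Section 12.2 gives one analysis for arm 1: "Positive and negative predictive value of CGM diagnosis of hypoglycaemia as an outpatient or an inpatient vs 72 hour fast", and describes the fast as the gold standard. No other reference is named there for arm 1.

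Section 4 (Aims) defines arm 1 as "Investigation of patients suspected of having hypoglycaemia (spontaneous or reactive) alongside standard investigations", and the second objective in section 6.1 again covers both forms.

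Section 5 (Current standard of care tests) separates the two. For the reactive form, gold-standard "testing when reactive hypoglycaemia is suspected is with an extended oral glucose tolerance test or mixed meal test"; the 72-hour fast is given for the spontaneous form. The same paragraph says that the investigations try to reproduce the triggering situation but, "in particular for reactive hypoglycaemia, often fail to do so".

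Section 9 describes the planned arm 1 admission as "usually including an oral glucose tolerance test or mixed meal test, but certainly including a 72 hour fast".

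On purpose, the first objective in section 6.1 says of CGM: "This may exclude hypoglycaemia as a cause of symptoms and allow the patient to avoid a prolonged inpatient investigation". Section 5.4 hopes to "determine if blinded CGM testing can be used to obviate the need for inpatient testing".

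**The concern.** The reference in section 12.2 matches one of the two conditions under investigation. Take a patient with reactive hypoglycaemia whose fast is negative. If CGM picks up the lows at home, the patient is scored as a false positive; if CGM misses them, as a true negative. The protocol does not say that reactive patients have negative fasts. That is an inference from its naming a different test for them.

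The sentence quoted from section 6.1 contains two claims. NPV against the fast bears on sparing the patient an admission for a fast. It does not bear on excluding hypoglycaemia as the cause of symptoms in reactive patients, because a missed case improves the figure. Read as detection of any hypoglycaemia, PPV would be too low and, with an imperfect CGM, NPV too high. These are the only arm 1 results named in section 12.2, and section 12.1 looks ahead to CGM complementing or replacing inpatient investigation.

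**Working it through.** **Text.** The conflict needs no arithmetic. Section 5 has two gold standards by type, sections 4 and 6.1 enrol both types, and section 12.2 uses one standard for all. The protocol states no predictive value, so there is no figure to reproduce.

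**Where the mismatch applies.** It clearly reaches outpatient CGM, worn for five days of ordinary life before a planned admission and then compared with a fast. For inpatient CGM it depends on which hours are used. Section 9 says that "CGM monitoring will continue for the duration of their admission", which would take in a glucose tolerance or mixed meal test, but section 12.2 sets no window and section 6.3 ties the inpatient endpoint to the fast.

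**Size: an illustration in which every input is assumed.** The protocol gives 30 patients in total and no split by arm or type. Let arm 1 have N = 20, S = 6 spontaneous (all fast positive), R = 2, 4 or 6 reactive, and H = N − S − R without hypoglycaemia (12, 10 or 8). Let f be the share of reactive patients with a positive fast and t the share found by the glucose tolerance or mixed meal test, independent of the fast. The formal diagnosis then finds r = 1 − (1 − f)(1 − t) of reactive cases.

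Error-free CGM: PPV against the fast = (S + fR)/(S + R); PPV against the formal diagnosis = (S + rR)/(S + R). With f = 0, r = t. Numerators are expected counts:

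| R | PPV vs fast (exact 95% CI) | Formal diagnosis, t = 0.25 | Formal diagnosis, t = 0.75 | Gain, points |
|---|---|---|---|---|
| 2 | 6/8 = 75% (35–97) | 6.5/8 = 81.25% | 7.5/8 = 93.75% | 6.25–18.75 |
| 4 | 6/10 = 60% (26–88) | 7/10 = 70% | 9/10 = 90% | 10–30 |
| 6 | 6/12 = 50% (21–79) | 7.5/12 = 62.5% | 10.5/12 = 87.5% | 12.5–37.5 |

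The gain is (r − f)R/(S + R) = (1 − f)tR/(S + R). At f = 0.5 it halves, and PPV against the fast is 7/8 = 87.5%, 8/10 = 80% and 9/12 = 75%. At f = 1 it is zero.

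NPV moves only if CGM misses cases. With sensitivity and specificity both 0.9 (assumed) and f = 0, the number CGM negative is M = 0.9H + 0.1(S + R) = 11.6, 10.0 and 8.4.

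- NPV vs fast = (0.9H + 0.1R)/M: 11.0/11.6 = 94.8%, 9.4/10 = 94.0%, 7.8/8.4 = 92.9%.
- NPV vs formal diagnosis = (0.9H + 0.1(1 − t)R)/M. At t = 0.25: 10.95/11.6 = 94.4%, 9.3/10 = 93.0%, 7.65/8.4 = 91.1%. At t = 0.75: 10.85/11.6 = 93.5%, 9.1/10 = 91.0%, 7.35/8.4 = 87.5%.

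The NPV shift is thus about 0.4 to 5.4 points. Even 8 correct out of 8 has an exact 95% interval of 63–100%.

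**The case against.** The fast can be defended. It is the one test that a planned arm 1 admission is certain to include, whereas the glucose tolerance or mixed meal test is only usual. A single reference applied to everyone avoids partial verification. Section 5.4 argues largely from the burden of inpatient fasts, and predictive values against the fast answer whether CGM could spare patients that. All of this stands: for that aim, all that is missing is a label. It does not cover the other half of the first objective, and section 12.2 speaks of diagnosing hypoglycaemia, not of predicting a fast.

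Reactive detection is also not left unassessed. Section 6.3 makes capture of finger-prick episodes an endpoint, and section 8 matches CGM with finger-prick and laboratory glucose. A true low is still credited there. This limits the harm but does not change what the patient-level PPV and NPV measure.

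A reader might infer that even a CGM low confirmed during an inpatient glucose tolerance or mixed meal test must count as a false positive. The documents do not support that: with the window unset and the inpatient endpoint tied to the fast, such a low may lie outside the comparison.

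A reader might also expect only the larger PPV gains. Section 5 says that the tests often fail for the reactive form, and section 9 does not guarantee them, so a yield as low as 25% belongs in the range.

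**Conclusion.** The point holds, within limits. Section 12.2 fixes a reference that the protocol elsewhere assigns to one of the two conditions in arm 1. Since the section states the reference outright, this is not a detail left for a later analysis plan. The fast-based values are valid as prediction of the fast result. They are not valid evidence that CGM excludes hypoglycaemia of either type.

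The direction (PPV too low and, if CGM misses cases, NPV too high) rests on at least some reactive patients having a negative fast. The size rests wholly on assumed inputs: PPV understated by about 6 to 37.5 points across the cases shown, less if some reactive fasts are positive, and not at all if all are. The NPV shift is small beside the imprecision.

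It would go too far to conclude that the arm 1 results as a whole are unsound, as the episode-level comparisons are untouched. In a 30-patient feasibility pilot with no decision threshold, the harm lies in how the predictive values will be read. Severity is minor to moderate.

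**What to change.** Reword the arm 1 part of section 12.2:

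1. Label PPV and NPV against the 72-hour fast as prediction of the fast result.
2. Add PPV and NPV against the formal diagnosis after inpatient investigation (section 15.2), as the reference for hypoglycaemia of either type. Require it to be recorded before the arm 1 CGM data are reviewed. Review is a more workable cut-off than download: section 9 puts the download at the end of the inpatient investigations and section 15.2 puts the diagnosis after them. It keeps the reference blind to CGM, consistent with section 13.
3. Where the type is recorded, give the number detected by CGM out of the number diagnosed, by type. Report how many fast-negative patients had no glucose tolerance or mixed meal test, and give the pooled values with these patients counted as negative and with them left out.

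Keep the episode-level matching of sections 6.3 and 8 as a separate analysis.

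The cost is a few sentences and a record that the diagnosis preceded CGM review. The formal diagnosis and laboratory results are already source data, so no new test, visit or patient is needed. The limits should be stated: verification of the reactive form is partial, the formal diagnosis rests on tests that the protocol calls fallible, and counts by type will be small (4 detected of 4 has an exact 95% interval of 40–100%).

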7.2 Exclusion criteria

Unwilling or unable to give consent
Unable to speak sufficient English to give consent and understand study requirements
Age<18
Lack of capacity to consent
Underlying hepatic condition

Current excessive alcohol consumption (men regularly consuming >50 units/week, women >35 units/week)

Current use of Diabetic medication or insulin

Currently pregnant

Any patient on haemo or peritoneal dialysis

8. Study design

Arm 1

Patients will be recruited to the study via the endocrine outpatient clinic, or via referral to St Bartholomew's hospital for inpatient management of hypoglycaemia.

For those originating from the outpatient department, patients will receive a CGM kit, finger prick testing meter and glucose monitoring diary.

5 days prior to admission to hospital the patient will start the continuous glucose monitoring and will also record their finger prick glucose reading in their glucose monitoring diary at any point they experience symptoms they ascribe to hypoglycaemia.

During their admission to hospital for investigation into suspected hypoglycaemia (either patients from outpatients, or direct admissions), patients will continue/start continuous glucose monitoring, alongside standard of care twice daily venous glucose, insulin and c-peptide measurements and routine finger prick testing. As per standard of care, extra finger prick glucoses and venous glucose/insulin/c-peptide testing will be performed when the patient experiences symptoms that they associate with hypoglycaemia.

Arm 2

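### Arm 1 analysis plans only PPV and NPV, which depend on prevalence as well as CGM accuracy and do not estimate the capture endpoints in 6.3; P<0.05 has no Arm 1 null value

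*Protocol*

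**What the plan says.** Protocol section 12.2 opens with a general threshold, "P<0.05 will be considered statistically significant". Its only Arm 1 entry is "Positive and negative predictive value of CGM diagnosis of hypoglycaemia", for outpatient or inpatient CGM, set against the 72-hour fast, with the fast named as the gold standard. No null value, target value, comparator or test is given for Arm 1. The only test named in the section belongs to Arm 2: "within patients (blinded vs unblinded phase) using paired T test".

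Other sections bear on this:

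- **6.3 (primary endpoint, Arm 1).** As an outpatient, CGM should reflect the finger-prick readings, capture finger-prick-confirmed episodes, and detect hypoglycaemia during sleep. As an inpatient, CGM should call hypoglycaemia when the finger-prick or laboratory glucose does.
- **6.2 (secondary objective).** Whether CGM records hypoglycaemia accurately.
- **6.1 (first objective).** CGM before admission might exclude hypoglycaemia and spare the patient a long inpatient work-up.
- **8 (study design).** Arm 1 patients arrive "via the endocrine outpatient clinic, or via referral to" the hospital as inpatients. The share from each route is not fixed. CGM is also to be matched to finger-prick and laboratory glucose to check concordance.
- **12.1.** The sample size is 30 over both arms, justified as follows: "This is intended to be a pilot study to test the feasibility of using CGM for this purpose". On later use of CGM it adds: "It may in future complement (or in some instances replace) inpatient investigation of hypoglycaemia".

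**The concern.** The planned measures and the stated endpoints run in opposite directions. Section 6.3 starts from a reference-positive result and asks whether CGM agrees, which is a sensitivity question. PPV and NPV start from the CGM result and ask whether the reference agrees. The second pair cannot be read as an answer to the first, because prevalence lies between them.

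At stake is how the main Arm 1 result will be read. If CGM may later replace some inpatient investigation, readers will want to apply the result to patients whose prevalence differs from this sample's. A bare NPV gives them no means of doing so and could be taken for a fixed property of the device. With so few patients, a predictive value without an interval is also easy to over-read. Finally, a significance threshold with no null value lets significance for Arm 1 be defined after the data are seen.

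**Working it through.** **The plan's own figure.** The 30 in section 12.1 comes with no power, effect size or precision target, so there is nothing to reproduce.

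**Inputs.** The protocol gives no patient-level sensitivity (se) or specificity (sp) of CGM against the fast, and no prevalence (p). All values below are assumptions for illustration.

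**1. Dependence on prevalence, with accuracy held fixed (se = sp = 0.85).**

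PPV = se·p / [se·p + (1 − sp)(1 − p)]

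NPV = sp(1 − p) / [sp(1 − p) + (1 − se)p]

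- p = 0.20: PPV = 0.17/(0.17 + 0.12) = 0.586; NPV = 0.68/(0.68 + 0.03) = 0.958.
- p = 0.60: PPV = 0.51/(0.51 + 0.06) = 0.895; NPV = 0.34/(0.34 + 0.09) = 0.791.

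The device is identical in both lines. Sensitivity, which is closest to what 6.3 asks for, is 0.85 in both.

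**2. Dependence on accuracy, with prevalence held fixed (p = 0.30).**

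- se = sp = 0.5: PPV 0.300, NPV 0.700.
- se = sp = 0.7: PPV 0.500, NPV 0.845.
- se = sp = 0.9: PPV 0.794, NPV 0.955.

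Both factors matter.

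**3. Where the recruitment route can enter.** Under section 9, a directly transferred patient has CGM fitted during the admission and so contributes no outpatient CGM. The balance of routes can therefore move only an inpatient or a pooled estimate. Suppose clinic patients had p = 0.2 and transfers p = 0.7, with se = sp = 0.85. As the share of transfers in such an estimate rises from 0% to 50% to 100%, p goes from 0.20 to 0.45 to 0.70, PPV from 0.586 to 0.823 to 0.930, and NPV from 0.958 to 0.874 to 0.708.

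**4. The P<0.05 rule without a null value.** Suppose 9 of 10 CGM-positive patients are confirmed by the fast. The one-sided exact binomial P, Pr(X ≥ 9 | n = 10, π0), is:

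- π0 = 0.5: 0.011
- π0 = 0.7: 0.149
- π0 = 0.8: 0.376
- π0 = 0.9: 0.736

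The same result is significant or not depending on a value the protocol does not state.

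**5. Precision.** The denominators are assumed, because the 30 patients are not divided between the arms. With all n correct, the exact (Clopper-Pearson) lower 95% limit is 0.025^(1/n).

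- 10 of 10: 0.025^(1/10) = 0.692.
- 30 of 30: 0.025^(1/30) = 0.884. This would need every patient in the study to fall in one denominator.
- 9 of 10: exact 95% interval 0.555 to 0.997.

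**The case against.** The strongest reply is that PPV and NPV suit the purpose. The first objective in 6.1 is to rule hypoglycaemia out before admission, and NPV among consecutive referrals answers that directly. This stands, and NPV should stay. Sensitivity and specificity can also vary with case severity, so adding them does not remove every effect of referral. That stands too.

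It can also be said that intervals and extra measures are usual content for an analysis plan, and that this is a feasibility pilot. Missing detail alone would indeed be no finding. But the choice of measure and the P threshold are fixed in this protocol, which also says in section 12 that no statistician need be involved.

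Four stronger readings are tempting and are not supported:

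- A reader might infer that the patient mix, and not CGM, determines PPV and NPV. Step 2 shows that accuracy moves them just as plainly.
- A reader might infer that Arm 1 as a whole is judged only by PPV and NPV. That is true of 12.2. Section 6.3 sets capture endpoints and section 8 plans a concordance check, but 12.2 gives them no Arm 1 analysis.
- A reader might infer that transfers contaminate the result for clinic patients. Outpatient CGM comes from clinic patients alone, and 12.2 does not say that the two settings are pooled. Nor does the protocol say that prevalence differs by route. Section 8 does describe referral "for inpatient management of hypoglycaemia", but sections 8 and 9 go on to treat both groups as under investigation for suspected hypoglycaemia.
- A reader might infer that the P<0.05 rule is empty throughout. It has a use in the Arm 2 paired comparison.

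**Conclusion.** The point holds in a limited form. Section 12.2 gives Arm 1 two measures that mix CGM accuracy with prevalence and do not estimate the capture and concordance endpoints in 6.3 or the accuracy objective in 6.2. Its significance threshold has nothing to act on in Arm 1.

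Under the assumed 85% sensitivity and specificity, a change in prevalence from 20% to 60% moves NPV by about 17 percentage points (95.8% to 79.1%) and PPV by about 31 (58.6% to 89.5%). The direction does not depend on the assumption, provided CGM is imperfect but informative; the size does.

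The data to be collected are sound for this purpose. The fault lies in what is planned to be reported from them, so the change is worth making but the study does not depend on it.

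**What to change.** In section 12.2:

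1. Add sensitivity and specificity of CGM diagnosis against the 72-hour fast, with exact 95% confidence intervals, from the same patient-level 2x2 table.
2. Keep PPV and NPV, also with exact 95% intervals. Report them separately for outpatient CGM and inpatient CGM, not pooled, and state the observed prevalence beside each.
3. Confine the P<0.05 threshold to the Arm 2 comparisons.

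This takes a few sentences and no new data. The cost is that the intervals will be visibly wide, as the 69% lower limit for 10 of 10 shows. One limit remains: patient-level sensitivity runs in the same direction as the 6.3 endpoints but does not count individual episodes, so it should not be presented as an episode capture rate. A further split by recruitment route is optional, since with at most 30 patients the cells would be very small.
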